3.3.2.5 Mortality

Death that occurs after the first dose of ISIS 420915 will be analyzed as follows:

Time from **Day 1 of ISIS 420915** to the date of death for LSS and time from **CS3 Study Day 1** to the date of death for SS will be summarized for the patients that met the criterion using the following descriptive statistics: mean, standard deviation, median, P25, P75, and minimum and maximum.

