3. EXPERIMENTAL PLAN

3.1 Study Design

This is a multicenter open-label study. Eligible patients who have satisfactorily completed ISIS 420915-CS2 will receive 300 mg ISIS 420915 once weekly for 156 weeks (3 years). Exceptions will be given to patients that had a dose reduction or schedule change in ISIS 420915-CS2 who may continue with the same dose level or schedule in this study. All patients will receive supplemental doses of the recommended daily allowance (RDA) of vitamin A.

If at the end of 3 years of treatment, ISIS 420915 is not commercially available in the country of the patient, the patient may continue to receive treatment in this study for up to 2 years more or until ISIS 420915 becomes commercially available in the patient's country, whichever occurs earlier. At the end of the 5 years of treatment with ISIS 420915 in this study, if ISIS 420915 is not commercially available, patients may be allowed to continue receiving treatment with ISIS 420915 via an early access route to be defined by the sponsor and depending on local regulations. After completing the treatment period, patients will enter the 3-month post-treatment evaluation period. If a patient discontinues treatment in this study, but is continuing to receive treatment with ISIS 420915 via another mechanism, the entry of the patient into the 3-month post-treatment evaluation period may be omitted.

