3.4.3 Post-Treatment

After completion of treatment, patients will enter a 3-month post-treatment evaluation period that consists of clinic and non-clinic visits for safety monitoring.

If a patient discontinues treatment in this study, but is continuing to receive treatment with ISIS-420915 via another mechanism, the entry of the patient into the 3-month post-treatment evaluation period may be omitted.

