- o For both studies the post-treatment period starts on the day after the treatment period and ends on the day of the patient's last contact date within the study.

• For safety endpoints except for ERG:

- The on-treatment period for the parent study spans the time during which the study treatment is administered from the CS2 Study Day 1 until 7 days after the last dose of medication in the parent study. The on-treatment period for the OLE study is from the CS3 Study Day 1 until 7 days after the last dose of medication in the OLE study.
- For both studies the safety post-treatment period starts on the day after the safety treatment period and ends on the day of the patient's last contact date within the study.
- For both studies the Safety on-study period spans the time drug is first administered until the day of the patient's last contact date within the study.
- The period for the longitudinal safety analysis spans the time from the first dose of ISIS
 420915 in the parent study and ends on the day of the patient's last contact date within the study. The subject's last contact date is defined as follows:
 - (1) for subjects who signed an informed consent form in the OLE study, it is the last contact date within the OLE study;
 - (2) for subjects who did not sign an informed consent form in the OLE study but had been administered ISIS 420915 in the parent study, it is the last contact date within the parent study. The details of longitudinal safety analysis for AEs and safety lab results will be addressed in section 3.3.

For ERG:

The on-treatment period for the parent study spans the time during which the study treatment is administered from the CS2 Study Day 1 until 28 days after the last dose of medication in the parent study. The on-treatment period for the OLE study is from the CS3 Study Day 1 until 28 days after the last dose of medication in the OLE study.

- For both studies the safety post-treatment period starts on the day after the safety treatment period and ends on the day of the patient's last contact date within the study.
- The PK on-study period for the OLE study spans the time ISIS420915 is administered in the OLE study (CS3 Study Day 1) until the day of the patient's last contact date within the OLE study.

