3.2.1.4 Data Summary Plan

The table below details what data will be included in the summary and analysis output by endpoint type. Data summarized or analyzed at each interim analysis will be based on data collected up to the data cut date. It is possible that on-treatment data and post-treatment data available for each interim analysis is different from the final analysis at the end of study because data collected after each interim analysis data cut may slot into different treatment period. Outputs will be updated for each interim analysis and for the final analysis. In select instances the data for a type of endpoint that is summarized or analyzed may not be consistent with the rules in the table below; such exceptions will be noted in this document.

Endpoint type	Output type	Comment/definition
Efficacy	-Listings -On-treatment (CS2&CS3) summary/analysis tables -Post-treatment summary tables	-On-treatment (CS2 period):The CS2 Study Day 1 S Date of assessment S Last dose date in parent study+ 52 days -On-treatment (CS3 period): CS3 STUDY DAY 1 \$ Date of assessment S Last dose date of OLE study+ 52 days -showing both CS2 visits and CS3 visits. Note the results of the analyses at the CS2 visits will not be the same as the results from the CS2 study as this table only includes patients in the CS3 FASPost-treatment: Date of assessment > last dose date of OLE study + 52 days -Visit defined by analysis visit window
PD, BMIand mBMI	-Listings -On-treatment (CS2&CS3) summary/analysis tables -Post-treatment summary tables	-On-treatment (CS2 period): The CS2 Study Day 1 S Date of assessment S Last dose date in parent study+ 28days -On-treatment (CS3 period): CS3 STUDY DAY 1 S Date of assessment S Last dose date of OLE study+ 28days -showing both CS2 visits and CS3 visits. Note the results of the analyses at the CS2 visits will not be the same as the results from the CS2 study as this table only includes patients in the CS3 FAS.

Endpoint type	Output type	Comment/definition
		-Post-treatment: Date of assessment> last dose date+ 28days -Visit defined by analysis visit window
Safety Endpoints: ECG, Lab, vitals sign (including body weight)	-Listings -On-treatment summary tables (CS3) -Post-treatment summary tables	-On-treatment (CS3 period): CS3 Study Day Is Date of assessment 5 Last dose date + 7 days -Post-treatment: Date of assessment> last dose date+ 7 days -Visit defined by analysis visit window

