3.2.2 Patient Populations Analyzed

The following analysis populations are defined for this present OLE study:

- Screened patients will be defined as patients who signed an informed consent form.
- Enrolled patients will be defined as patients who signed an informed consent form and were not screen failures.
- The FAS will include all enrolled patients who received at least 1 injection of ISIS420915 in the
 OLE study and who have at least one post-baseline efficacy assessment for the mNIS+7 score or
 Norfolk QOL-DN questionnaire total score collected after CS3 Study Day 1 in this OLE study. This
 will be the primary population for analysis of efficacy and PD outcomes.
- The Safety Set (SS) will include all enrolled patients who received at least 1 injection of ISIS
 420915 in the OLE study. This population will beused for analyses of all safety measures
 collected in this OLE study. Results will be summarized under the treatment which the patients
 received in the parent study.
- The Longitudinal Safety Set (LSS): will include all patients who received at least 1 injection of ISIS 420915 in the parent study. This population will beused for the longitudinal safety analysis for either the parent study or this OLE study. Results will besummarized under the treatment which the patients received in the parent study. Note that this population will include patients who receive ISIS 420915 in the parent study but did not enter this OLE. It does not include patients who took placebo in CS2.
- The PPS will include the subset of the Full Analysis Set that have received at least 70% of the prescribed doses of ISIS 420915 in this OLE study and that have no significant protocol deviations in the OLE study that would be expected to affect efficacy assessments. Prescribed doses of ISIS420915 mentioned above is defined as the total assigned dose in mg from the Week 1 to the last dose within this study up to week 156 (first three years), i.e. 300mg*156 doses= 46800mg. Patients in FAS of this OLE study but excluded from PPS in the parent study will be excluded from the PPS in this OLE study as well. This will be a secondary population for

efficacy and PD analyses. The detailed criteria and definitions for major protocol violations will be specified. Results will be summarized under the treatment which the patients received in the parent study.

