Time from **CS3 Study Day 1** to the onset of each of these events collected in the OLE study will be summarized for the patients in SS that met the criterion. Summaries including the following descriptive statistics: mean, standard deviation, median, P25, P75, and minimum and maximum.

Kaplan-Meier plots for time to first event will also be provided for value < 140×10^9 /L, value < 100×10^9 /L and value < 75×10^9 /L.

The post-baseline nadir (absolute value, change from the **ISIS 420915 baseline**, and percent change from the **ISIS 420915 baseline**) of platelet count will be summarized by treatment group of the parent study.

Duration of platelet counts below the $140 \times 10^9/L$ will be summarized, based on the duration (in weeks) each patient was below the $140 \times 10^9/L$.

The above analyses will be repeated for the subgroups defined by CM-ECHO Set.

Scatter plots for nadir platlets versus the **ISIS 420915 baseline** of BMI, mBMI, and weight will be provided.

A listing of patients with dose pause due to Platelet < 75 x10^9/L will also be provided.

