5.3 Interim Analysis II

CS3 Initerim analysis II are based on the data as of the data cutoff date of 31-MAY-2018. The following data were included in the interim analyses: dispositions, demographics, concomitant medications, exposure, adverse events (AEs), laboratory results, ECHO, mNIS+7, NIS, NIS-LL, Norfolk SF36, and PND score.

The table below lists what data will be included in the summary output by endpoint type and what output is planned for this interim analysis II.

Provided at interim II	Comment
Patient Characteristics (for CS3 and ISS)	
 Summary of demographic characteristics and baseline characteristics (excluding efficiacy endpoints) and exposure to Study Drug. 	- For SS
Concomitant medication.	- On-study summary for SS
Listings for exposure, dropouts and dose pause	

Provided at interim II	Comment
Safety Endpoint (for CS3 and ISS)	
Summary tables for AE.	- On-Study for SS
Summary tables of safety lab (Hematology, Chemistry) by visit.	- On-Treatment+ Post-Treatment for SS
 Summary table and shift table of abnormal safety lab results and stopping rules. 	- Abnormal safety lab is on-study for SS
Survival plot for time from first ISIS dose to death or discontinuation	- On-Study for SS
 Listing of adverse events and medication occurred or took 30 days prior to platelet value <50x10⁹/L 	
 Listing of platelet values and anticoagulants or antiplatelets medication for subjects with grade 3 thrombocytopenia 	
Efficacy (for CS3)	
Summary table of mNIS+7, NIS, NIS-LL, SF-36 and PND score, NT-proBNP and Log-Transformed NT- proBNP	- On-treatment for FAS
Listing of NSC domain, subdomain and totalscore	- CS3 Enrolled Patients
PD Parameters (for CS3)	
Summary of TTR and RBP4 by visit.	- On-treatment for FAS
ECHO (for CS3)	
Global Longitudinal Strain and Global Left Ventricular Size and Function - LV Mass	- On-treatment for Enrolled Patients and CM-ECHO Set

Interim II also create Topline efficacy/safety tables by subgroup/subset for CS3 (both efficacy and safety outputs) and ISS (safety outputs). The subgroup/subset are:

- Stage 3 patients (PND score=V at BL)
- V30M TTR Mutation (IVRS)
- Disease Stage (IVRS)
- Previous Treatment (IVRS)
- CM-ECHO Set

- NT-proBNP>650 pg/nL at BL
- NYHA 1 vs 2 at BL
- IVS>15 mm at BL
- Paitents who Diagnosed as TTR Cardiomyopathy at BL
- Efficacy of patients who had pauses vs those who didn't
- Patients who had pauses vs those who didn't (for primary endpoints only)

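### SAP 3.3.2.5 summarizes time to death only among patients who died; with unequal follow-up this does not estimate mortality risk, and no censored analysis of death alone is stated

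*Combined protocol and SAP*

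**What the plan says.** SAP 3.3.2.5 takes time to death from CS3 Study Day 1 for the Safety Set (SS) and from Day 1 of ISIS 420915 for the Longitudinal Safety Set (LSS). It "will be summarized for the patients that met the criterion using the following descriptive statistics: mean, standard deviation, median, P25, P75" and the minimum and maximum. SAP 3.3.2.6 and 3.3.2.7 refer back to this section and add no method.

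Follow-up is unequal by design:

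- **Country.** Protocol 3.1 sets 156 weeks of treatment. Where the drug is not commercially available at that point, "the patient may continue to receive treatment in this study for up to 2 years more", to a maximum of 260 weeks.
- **Discontinuation.** Post-treatment follow-up is 3 months, but if the drug continues by another route "the entry of the patient into the 3-month post-treatment evaluation period may be omitted" (Protocol 3.4.3). Withdrawal of consent ends observation at once, and a liver transplant requires withdrawal (Protocol 8.9).
- **Analysis set.** LSS starts in the parent study and includes "patients who receive ISIS 420915 in the parent study but did not enter this OLE" (SAP 3.2.2).

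The one survival display involving death is in SAP 5.3: "Survival plot for time from first ISIS dose to death or discontinuation". For platelet thresholds, by contrast, SAP 3.3.4.2 says that "Kaplan-Meier plots for time to first event will also be provided".

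**The concern.** Safety and tolerability are the primary objective. A mean or median time to death computed only in those who died has no survivors in it and no person-time. With unequal follow-up, a later average death can reflect fewer early deaths, longer observation or a hazard that rises with time, and the summary cannot tell these apart. Someone who wants the risk of death over 3 to 5 years, or who sets SS beside LSS or one data cut beside another, would find no stated output that answers the question. The composite plot does not fill the gap, because stopping treatment for any reason counts as an event alongside death.

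**Working it through.** **Inputs from the documents.** OLE treatment of 156 weeks, or up to 260 (Protocol 3.1, 3.4.2); 3 months of post-treatment follow-up (3.4.3); 65 weeks in the parent study (2.4); about 135 patients potentially eligible (3.3). The documents give no death rate, discontinuation rate or expected number of deaths, so there is no figure of the plan's own to reproduce.

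**Assumptions.** Death hazard h of 2%, 4% or 8% per year, constant over time; discontinuation c of 15% per year (range 5-25%); share e entering Years 4-5 of 40% (range 20-60%); N = 135; no follow-up after treatment ends.

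**Step 1: the planned statistic.** Observed deaths at time t (years) have density h·exp(−(h+c)t), multiplied by e for 3 < t ≤ 5. Crude proportion dead = ∫f dt; decedent mean = ∫t·f dt / ∫f dt. At h = 0.04, h+c = 0.19:

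- Years 0-3: (1 − e^−0.57)/0.19 = 2.287
- Years 3-5: (e^−0.57 − e^−0.95)/0.19 = 0.941
- Crude proportion: 0.04 × (2.287 + 0.4 × 0.941) = 10.7%

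| h per year | c | e | Decedent mean (y) | Crude dead | 5-year risk, 1−e^(−5h) |
|---|---|---|---|---|---|
| 2% | 15% | 40% | 1.75 | 5.5% | 9.5% |
| 4% | 15% | 40% | 1.72 | 10.7% | 18.1% |
| 8% | 15% | 40% | 1.66 | 19.9% | 33.0% |
| 4% | 25% | 20% | 1.44 | 8.5% | 18.1% |
| 4% | 5% | 60% | 2.05 | 13.9% | 18.1% |
| 4% | 15% | 20% | 1.55 | 9.9% | 18.1% |
| 4% | 15% | 60% | 1.87 | 11.4% | 18.1% |

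Quadrupling the death rate moves the mean by 4.6 weeks (3.4 to 5.7 over the ranges of c and e). At a fixed 4% per year, the widest follow-up contrast moves it about 32 weeks, and Year 4-5 eligibility alone about 16 weeks. The crude proportion responds to the death rate but also shifts with follow-up.

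**Step 2: a simpler model.** With no discontinuation and everyone followed to T, the mean is 1/h − T·e^(−hT)/(1 − e^(−hT)). From h = 0.01 to 0.16 it runs from 1.61 to 1.48 years at T = 169 weeks (156 + 13) and from 2.59 to 2.26 at T = 273 weeks (260 + 13). Within LSS at h = 0.04 it is 0.74 years for someone followed only through the parent study (65 + 13 = 78 weeks) and 3.10 years at the longest possible follow-up (65 + 260 + 13 = 338 weeks).

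**Step 3: drop the constant hazard.** Take a Weibull cumulative hazard (t/s)^k with s = 5/0.20^(1/k), so that 5-year risk stays at 1 − e^−0.20 = 18.1%. With c = 15% and e = 40%, the decedent mean is 1.35 years (k = 0.7), 1.72 (k = 1) and 2.21 (k = 1.5): about 45 weeks from timing alone, at the same 5-year risk.

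**Step 4: a censored measure.** Simulating a 4% per year hazard with 0-20% per year discontinuation, none, 30% or all followed to 5 years, and 13 weeks of follow-up after stopping, deaths per 100 patient-years stay between 3.99 and 4.01. The decedent mean in the same runs goes from 1.42 to 2.52 years and the crude proportion from 9.5% to 18.9%.

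**Step 5: precision of Kaplan-Meier.** Using Greenwood variance ∫h/R(t)dt with R(t) = 135·exp(−(h+c)t), multiplied by e from Year 3, and a log-log interval: at 2% per year, 9.5% at 5 years (95% CI 4-22%, about 23 at risk); at 8% per year, 33.0% (22-48%, about 17 at risk).

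**Step 6: informative censoring.** If the hazard is 4% per year on treatment but 8% after discontinuation, Kaplan-Meier reads 18.1-18.7% (0 or 3 months of follow-up after stopping) against a true 22.3%. At 12% after discontinuation it reads 18.1-19.3% against 25.9%.

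**The case against.** The case for leaving the section alone has real substance.

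- **The summary does what it says.** It claims only to describe when deaths occurred, and Step 3 shows that it carries timing information. This stands. A reader might infer that the statistic mostly tracks follow-up length; that holds under a constant hazard but not in general, because hazard shape alone can move it by more than the widest follow-up contrast.
- **Deaths are not hidden.** Counts would be visible under SAP 3.2.1, narratives of deaths are required (Protocol 10.6.2), and fatal treatment-emergent events also enter the exposure-duration groupings in SAP 3.3.2.6 and 3.3.2.7. This stands. None of these is a risk estimate.
- **The composite plot may reach the final report.** SAP 3.2.1.4 says "Outputs will be updated for each interim analysis and for the final analysis", and SAP 9.1 does not remove the plot, although 9.2 does not add it. Even if repeated, it is not an analysis of death alone.
- **Parent-study groups.** A reader might infer that comparing former placebo with former active patients is distorted. The documents do not support that: follow-up rules in SS do not depend on parent arm, and LSS contains no parent-study placebo patients.
- **Few deaths.** At 4% per year there would be about 14, with SD 1.22 years, so the mean has a standard error of 1.22/√14.4 = 0.32 years, about 17 weeks, as large as the eligibility shift. True, but this makes the mean no better as a measure of risk.
- **Kaplan-Meier is imperfect too.** Steps 5 and 6 concede wide late intervals and possible bias. The limits should be stated with the curve.
- **An unseen plan.** SAP 9.2.2 refers to an ISS SAP that was not available. It may already define mortality for the combined data.

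**Conclusion.** The point holds in limited form. The stated mortality summary does not estimate the risk of death, and no censored analysis of death alone appears in the protocol or SAP. On the base assumptions the decedent mean changes by under 5 weeks for a fourfold change in death rate, by about 32 weeks across the follow-up range, and by about 45 weeks across hazard shapes. Every rate used is an assumption, and the small response to the death rate was shown under a constant hazard. The near-insensitivity held across the hazards and follow-up lengths tried: in Step 2, a 16-fold change in hazard lowers the mean by 8% at 169 weeks and 13% at 273 weeks.

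The study is descriptive, so no error rate or power is at stake; the weight comes from safety being the primary objective. A reader might extend the criticism to the adverse-event tables. The documents do not support that as it stands: the SAP prescribes no particular denominator for the exposure bands, requires denominators to be shown, and plans a plot of incidence rates for common events. This is an improvement that should be made, not a flaw that undermines the study.

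**What to change.** In SAP 3.3.2.5:

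1. Report deaths as n/N for each analysis set.
2. Add Kaplan-Meier cumulative mortality by year, with 95% CI and numbers at risk, for SS from CS3 Study Day 1 and for LSS from Day 1 of ISIS 420915. Censor at the last contact date in SAP 3.2.1.1.4: for those who consented to the extension, "it is the last contact date within the OLE study"; otherwise, the last contact in the parent study.
3. State that the curve estimates mortality while followed, that late intervals will be wide, and that censoring at discontinuation or liver transplant may be informative. Add a sensitivity analysis of death or liver transplant.
4. Say whether the death-or-discontinuation plot from Interim Analysis II is repeated at the final analysis.
5. If the ISS SAP already defines such an analysis for the combined data, cross-refer to it.

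The existing description of timing among those who died can stay beside the curve. The cost is SAP wording, one figure with a numbers-at-risk row and a few table columns. The dates needed are already required by the SAP's own definitions, and Kaplan-Meier is already planned for platelets.

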3.3.2.6 OLE Study Analysis of TEAEs

TEAEs which occur during the OLE study include TEAEs which first occurred or worsened on or after **CS3 Study Day 1**. Derivation is described in Section 3.3.2.

The following categories of AEs in the OLE study will be summarized by treatment group from the parent study: all TEAEs; TEAEs leading to early discontinuation from Study Drug or from the study; and serious adverse events. The percentage of patients reporting the adverse event will be summarized by MedDRA System Organ Class (SOC) and Preferred Term (PT), and will be sorted by SOC alphabetically and then by decreasing frequency of PT within SOC.

Summaries of drug related TEAEs, TEAEs by maximum severity, TEAEs grouped by duration of exposure to the Study Drug at the start of the event (< 6 months, \geq 6 months to < 12 months, \geq 12 months to < 24 months, \geq 24 months to < 36 months, \geq 36 months to < 48 months, \geq 48 months to < 60, \geq 60 months) and Number of dose at the start of event (<26, \geq 26 to < 52, \geq 52 to < 104, \geq 104 to < 156, \geq 156 to < 208, \geq 208 to 260, \geq 260) will also be provided. Duration of exposure and the number of doses is calculated from **CS3 Study Day 1** to the start date of event.

All TEAEs will be summarized for subgroups defined by the following variables:

- Age at parent study screening (<65 years and >=65 years),
- Sex (Female and Male),
- Race (White, non-White),
- Region (North America, Europe and South America / Australasia),
- CM-ECHO Set (Included and Not Included).

As well as stratification factors at randomization during the parent study, including

- V30M TTR mutation (Yes, No),
- previous treatment with Vyndagel® or Diflunisal (Yes, No),
- Disease stage (Stage 1 and Stage 2).

Results will not be provided for a variable if the overwhelming majority of patients are within one level of the subgroup. Non-TEAEs reported will be flagged in the all AE listing.

TEAEs in the following categories will also be summarized in tables and listed separately:

- Adverse events of special interest (defined in section 3.3.2.1)
- Other adverse events of interest (defined in section 3.3.2.2)
- Local cutaneous reactions at injection site (defined in section 3.3.2.3)
- Flu-like reactions (defined in section 3.3.2.4)

Summary tables of the number and percentage of patients with these adverse events will be displayed split by AE category and treatment group received in the parent study.

Mortality defined in section 3.3.2.5 on SS will be summarized.

A plot of incidence rates and relative risks for common TEAEs, with an incidence of 5% or more, by treatment group assigned in the parent study will be provided.

Summary of non-serious common TEAEs, with an incidence of 5% or more, will be presented by Preferred Term.

Summary tables of the number and percentage of patients with drug related bleeding TEAEs will be presented by bleeding location and Preferred Term.

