8.9 Withdrawal of Patients from the Study

Patients must be withdrawn from the study for any of the following:

- Withdrawal of consent
- The patient is unwilling or unable to comply with the protocol
- The patient receives a liver transplant

Other reasons for withdrawal of patients from the study might include:

- At the discretion of the Investigator or Sponsor for medical reasons
- At the discretion of the Investigator or Sponsor for noncompliance
- Significant protocol deviation
- Administrative decision by the Investigator or Sponsor
- ISIS 420915 becomes commercially available in the local country (patients in Year 4 or Year 5)
- ISIS 420915 is rejected by the regulatory authority in the local country

All efforts will be made to complete and report the observations as thoroughly as possible up to the date of withdrawal. All information, including the reason for withdrawal from Study, must be recorded in the eCRF.

Any patient who withdraws consent to participate in the study will be removed from further treatment and study observation immediately upon the date of request. Patients withdrawn for any reason should be encouraged to complete the ET visit at the time of withdrawal (Appendix A).

Patients who receive a liver transplant should be encouraged to return to the clinic to complete the ET visit as soon as feasible after the transplant procedures.

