10.2 Sample Size Considerations

No sample size calculations were performed as this is an extension study to the double-blind, placebo-controlled ISIS 420915-CS2 study. Approximately 135 patients are planned in the ISIS 420915-CS2 study and may be eligible to enroll into this study.

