1.1 Study Overview

Transthyretin (TTR) is synthesized primarily in the liver and is secreted into the plasma as a 55 KD protein composed of four identical subunits of 14 KD each. A major function of TTR in the plasma is to transport retinol (vitamin A) to tissues through an association with Retinol binding protein 4 (RBP4). Transthyretin amyloidosis is a rare hereditary disease caused by mutations in the TTR protein. The disease-causing mutations destabilize the normal tetrameric structure of TTR causing its dissociation into free monomers and subsequent aggregation into insoluble fibril deposits.

These deposits are found in multiple organs including the peripheral nervous system, gastrointestinal tract and heart. They result in local damage to cells leading to a peripheral polyneuropathy (called Familial Amyloid Polyneuropathy or FAP) and a cardiomyopathy (called Familial Amyloid Cardiomyopathy or FAC). FAP can be classified into 3 stages of disease based on ambulatory status: Stage 1 – do not require assistance with ambulation; Stage 2 – require assistance with ambulation; Stage 3 – wheelchair bound (Coutinho et al. 1980). The total worldwide prevalence of FAP has been estimated at approximately 10,000 patients (Coelho et al. 2008).

ISIS 420915 is an antisense drug targeted to human TTR mRNA and its hybridization to the cognate TTR mRNA results in the RNase H-mediated degradation of the TTR mRNA, thus preventing production of the TTR protein.

ISIS 420915-CS2 (the parent study) is a Phase 2/3 multicenter, double-blind, placebo-controlled study to assess the efficacy and safety of ISIS 420915 in patients with FAP. The study plans to enroll approximately 135 patients randomized 2:1 (90 ISIS 420915 to 45 placebo) to receive 300 mg ISIS 420915 or placebo. The study drug is administered 3 times during Week 1 and once weekly during Weeks 2 to 65.

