1.2 Objectives

1.2.1 Primary Objective

To evaluate the safety and tolerability of extended dosing with ISIS 420915 in patients with FAP.

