1.3 Hypotheses

There are no formal study hypotheses as this is an extension study to the double-blind placebo controlled parent study.

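### The main adverse event tables give crude percentages, and the relative-risk plot has no person-time basis, although follow-up is unequal and depends on country in Years 4-5; rates per 100 patient-years should be added.

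*Combined protocol and SAP*

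**What the plan says.** SAP 1.2.1 gives the primary objective: "To evaluate the safety and tolerability of extended dosing with ISIS 420915 in patients with FAP". For treatment-emergent adverse events (TEAEs) in the extension, SAP 3.3.2.6 states: "The percentage of patients reporting the adverse event will be summarized by MedDRA System Organ Class (SOC) and Preferred Term (PT". This covers all TEAEs, TEAEs leading to discontinuation, and serious events. Events of special interest (AESIs) and other events of interest are also shown as numbers and percentages of patients. SAP 3.3.2.7 follows the same pattern in the Longitudinal Safety Set, from first active dose in the parent study.

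SAP 3.3.2.6 also plans "A plot of incidence rates and relative risks for common TEAEs, with an incidence of 5% or more", by parent-study group. Neither section defines a person-time denominator. SAP 3.6.2, on immunogenicity, glosses incidence rate as a percent. Section 9 adds adverse event outputs but no exposure-adjusted rate.

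On follow-up, SAP 3.2.1.1.4 ends the on-study safety period at each patient's last contact. Protocol 3.1 and 3.4.2 plan three years of treatment, extended to at most 260 weeks where the drug cannot be obtained commercially. Protocol 8.9 lists as a possible reason for withdrawal "ISIS 420915 becomes commercially available in the local country (patients in Year 4 or Year 5".

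The plan does link some events to time or dose:
- TEAEs by exposure interval and dose count at onset (3.3.2.6, 3.3.2.7)
- Kaplan-Meier plots for three platelet thresholds (3.3.4.2)
- percentages of injections followed by local or flu-like reactions (3.3.2.3, 3.3.2.4)
- exposure in days, doses and milligrams (3.2.3)

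For the interval tables, 3.3.2.6 says: "Duration of exposure and the number of doses is calculated from" CS3 Study Day 1. SAP 3.3.2.7 starts the same count at Day 1 of ISIS 420915.

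**The concern.** A percentage of patients ever affected is a risk only over a stated period. Here the period differs by patient, so the same percentage can mean a common event seen briefly or a rare one seen for years. This matters in three places.

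- **Single-group statements.** A figure for long-term risk, quoted from these tables, has no time horizon.
- **Region subgroups.** Both sections split TEAEs by Region, while country decides who can enter Years 4-5. The COVID-19 addendum says that guidance went to centers with active patients, and the attached memo of March 2020 is addressed to Argentine and Brazilian sites. That fits late follow-up being concentrated in South America, although no counts are given.
- **The Longitudinal Safety Set.** It needs one active injection in the parent study and keeps patients who never entered the extension, alongside patients with up to 325 weeks of planned dosing.

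The SAP recognises the problem for efficacy: the responder analysis in 3.4.2.1 limits each visit to patients followed long enough to contribute. The adverse event tables have no counterpart.

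**Working it through.** **Design figures.** There is no planned precision or power to reproduce. SAP 1.3 says "There are no formal study hypotheses as this is an extension study", and Protocol 10.2 says "No sample size calculations were performed as this is an extension study to the double-blind, placebo-controlled ISIS 420915-CS2 study". The durations agree: 65 + 260 = 325 weeks (Protocol 2.4), and 65 + 156 = 221 weeks for the three-year plan (SAP 1.1). The parent study was "randomized 2:1 (90 ISIS 420915 to 45 placebo", which matches 135 split 2:1.

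**Assumptions.** The documents give no event rates and no follow-up by group or region. I assume constant rates h of 0.02 to 0.30 per patient-year and follow-up t of 6 weeks to 5 years. The 6-week end stands for early withdrawal and is not a stated figure.

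**Step 1: time horizon.** Crude proportion = 1 - exp(-h t). For example, 1 - exp(-0.10 x 3) = 25.9%.

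| h per patient-year | 6 weeks | 1 year | 3 years | 5 years | Ratio, 5 v 3 years |
|---|---|---|---|---|---|
| 0.02 | 0.2% | 2.0% | 5.8% | 9.5% | 1.63 |
| 0.05 | 0.6% | 4.9% | 13.9% | 22.1% | 1.59 |
| 0.10 | 1.1% | 9.5% | 25.9% | 39.3% | 1.52 |
| 0.30 | 3.4% | 25.9% | 59.3% | 77.7% | 1.31 |

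The last column compares two sets with the same true rate. The ratio of first events per person-time is 1.00 in every row.

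**Step 2: parent-study groups.** With equal rates, the crude ratio depends on the follow-up mix:
- same mix in both groups: 1.00
- 20%, 40%, 40% v 20%, 60%, 20% followed for 1, 3 and 5 years (mean 3.4 v 3.0 years): 1.07 to 1.13
- 15% v 35% stopping at 6 months, 55% v 35% followed for 3 years and 30% in each group for 5 years (mean 3.23 v 2.72 years): 1.18 to 1.19

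These mixes are illustrations, not estimates.

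**Step 3: a true difference.** With equal follow-up (20%, 50% and 30% at 1, 3 and 5 years) and a true rate ratio of 2, the crude ratio is 1.93, 1.83, 1.69 and 1.36 at lower-group rates of 0.02, 0.05, 0.10 and 0.30. Crude ratios for common events are pulled toward 1 even when follow-up is balanced.

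**Step 4: prior exposure.** Former-active completers enter with 65 weeks and 3 + 64 = 67 doses. Suppose the rate is 0.3 per year for the first 15 months on drug and 0.1 after that, with 3 years in the extension for everyone.
- Former placebo: 1 - exp(-(0.3 x 1.25 + 0.1 x 1.75)) = 1 - exp(-0.55) = 42.3%.
- Former active: 1 - exp(-0.1 x 3) = 25.9%.
- The crude ratio is 1.63 and the person-time rate ratio is 1.97.

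A rate ratio alone does not remove the effect of prior exposure.

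**Step 5: the interval clock.** A former-active patient's event in the first extension month falls under less than 6 months in the 3.3.2.6 table, although total exposure is about 16 months. In the 3.3.2.7 table the same event falls in 12 to less than 24 months.

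**The case against.** The study is descriptive, with no hypotheses and no concurrent control, and a percentage is a familiar first summary. The strongest objections concern how far the criticism reaches.

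- **The plan is not limited to crude percentages.** The interval tables, platelet plots, per-injection figures and exposure summaries are real. They are partial, though. Kaplan-Meier covers platelets only, per-injection figures cover two reaction types, and time to death is described only among those who died.
- **A reader might infer that the between-group relative risks are confounded by follow-up.** The documents do not support that as fact. Both parent-study groups come from a randomized trial, start at CS3 Study Day 1 and share the same duration and supply rules. Distortion would need different discontinuation or country mix.
- **A reader might infer that later exposure intervals will look falsely safe.** That would follow if the whole Safety Set were the denominator, but the SAP does not say so, and 3.2.1 requires tables to show their denominators. The fair request is to specify which one.
- **A reader might infer that prior exposure is ignored throughout.** SAP 3.3.2.7 already counts it for the former-active group, and for former placebo patients the 3.3.2.6 clock is already right. Only the labelling for former-active patients in 3.3.2.6 needs attention.
- **A separate plan may cover this.** SAP 9.2.2 draws on an integrated safety SAP that is not among these documents and may define exposure-adjusted rates. That cannot be checked, and 3.3.2.6 should in any case define its own terms.

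**Conclusion.** The point holds in a limited form. The main tables for TEAEs, serious events, discontinuations and AESIs are crude percentages over unequal follow-up, and the incidence-rate and relative-risk plot has no person-time basis. Under a constant rate of 0.10 per patient-year, the same risk process reads as 9.5%, 25.9% or 39.3% depending on whether patients are seen for 1, 3 or 5 years. Sets followed for 5 v 3 years differ by a ratio of 1.52 with no true difference in rate, or by 1.31 to 1.63 across rates of 0.30 down to 0.02. These sizes rest on assumed rates and follow-up.

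The Region subgroups and the Longitudinal Safety Set are the places where the plan's own rules make unequal follow-up likely. Between the parent-study groups, the built-in difference is about 65 weeks of prior exposure, not extension follow-up. This is a cheap improvement to the reporting of the primary objective.

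**What to change.** In SAP 3.3.2.6 and 3.3.2.7:

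1. Keep the percentages. For all TEAEs, serious events, events leading to discontinuation, AESIs and other events of interest, add patients with a first event per 100 patient-years at risk, with 95% CI. Cumulative incidence with numbers at risk is an acceptable alternative. End the person-time where the table's own counting period ends.
2. In 3.3.2.6, define incidence rate and base the plot on these rates and their ratios. Add a note that former-active patients enter with about 65 weeks of exposure, which a rate ratio does not remove.
3. In the exposure-interval and dose-count tables, use patients still exposed at the start of each interval as the denominator.
4. In 3.3.2.6 only, either count exposure and doses from Day 1 of ISIS 420915 (defined in 3.2.1.1.1) or label the intervals as extension exposure. SAP 3.3.2.7 needs no change on this.

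The dosing, onset and last-contact dates are already used in the SAP's derivations, so no new data are needed. The cost is SAP wording, programming and more table rows.
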